FIGURE 7. Topography and OCT based total power & topography maps. This figure shows that our recovered OCT based surfaces are sufficiently accurate to represent astigmatic information even in corneas altered by LASIK. Before LASIK (top row), topography and OCT are comparable (A & B). After LASIK (bottom row), topography (D) shows an effectively spherical cornea because it is only measuring the ablated anterior surface. In the OCT map (E), residual corneal astigmatism is still present (lighter blue) likely due to the unchanged astigmatic posterior surface (C & F). The measured spherical change pre to post LASIK was: $\Delta MRx = 5.25$ D, $\Delta topo = 3.94$ D, $\Delta OCT = 5.63$ D. The surgically induced change in astigmatism was: $\Delta MRx = 2.80$ D, $\Delta topo = 2.04$ D, $\Delta OCT = 2.63$ D. These maps show the central 5 mm of the cornea.

time was unreliable due to motion artifacts from slow acquisition [36]. Current clinical SDOCT is faster, but its limited depth range prevents measurement of the pertinent biometry values used in this formula. Our whole eye system is faster than SDOCT and has the depth range necessary to measure all the pertinent biometry values required to take advantage of this formula.

After undergoing cataract surgery with an intra-capsular posterior chamber IOL of the surgeon's choice, we will measure the manifest refraction at the final, post-operative month 1 visit. From this post-operative manifest refraction, the IOL power required to have achieved an emmetropic (plano) result will be calculated [45]. We will then compare this calculated reference power to the predicted power from the SoC and OCT methods and determine a prediction error for each. Given that IOLs are only powered in discrete increments of 0.50 D, a "good" clinical outcome should be within 0.50 D of the target. Hence, we will compare the proportion of subjects in the two groups (SoC and OCT) who have

prediction errors within ± 0.50 D of the calculated reference. Though finer discrimination than 0.50 D would be desirable, we are limited by the resolution of the IOL at ± 0.50 D steps. We cannot insert a lens that is 20.13 D, for example, if that is the theoretical suggested power. Reporting results within ± 0.50 D is also a standard accepted and used by the refractive surgical community [48].

From the literature, we can estimate the expected proportions for the SoC (P_{SoC}) and OCT (P_{OCT}) groups. Using the Haigis-L, the proportion of subjects who had a result within ± 0.50 D of the calculated reference was approximately $P_{SoC} = 41.98\%$ [45,49]. In a small pilot using averaged 2D corneal SDOCT measurements with less sampling than our 3D reconstructions, Tang et al. found the proportion of subjects with a result within ± 0.50 D of the calculated reference to be $P_{OCT} = 68.75\%$. Our null hypothesis is OCT will equal SoC ($H_0: P_{SoC} - P_{OCT} = 0$), and the alternate hypothesis is that OCT will be different ($H_A: P_{SoC} - P_{OCT} \neq 0$). Proportions will be compared using a conditional McNemar's test for paired proportions. Using the estimated proportions, $\alpha = 0.05$, and assuming zero correlation between pairs, we will need a minimum of 60 subjects to complete the study to have 80% power to detect a significant difference between these two proportions (PROC POWER, SAS v.9.3). If the correlation between pairs is 0.2, 60 subjects will provide 88% power; if the correlation is as high as 0.4, the power will be 96%. To account for possible enrollment losses from intra-surgical complications or follow-up losses, we will target an enrollment of 65 subjects over the project period to ensure that we will meet the minimum of 60 completed study subjects.

In addition to the primary outcome measure above, we will additionally report the mean absolute prediction error for the two groups. We will also repeat the optical biometry and OCT imaging post-operatively to further study the relationship between pre-operative biometry and the final IOL position (ELP). These measurements will allow us to further characterize the relationship between clinical optical biometry and the whole eye OCT pre- and post-operatively.

SA2. Expected Outcomes. We will have developed algorithms to accurately measure anterior segment biometry and corneal power with the whole eye OCT system. We will further have clinical data to support the idea that accurate measurement of anterior segment biometry will improve cataract surgery refractive outcomes in those who have previously had laser refractive surgery. While this growing population would particularly benefit because of the unique challenges presented by their altered corneas, the developed algorithms can also be applied for the larger group of cataract surgeries in those with normal corneas as well. Finally this aim also complements the posterior segment aim by independently validating the measurements of anterior segment surfaces by the whole eye OCT system.

SA2. Potential Problems & Alternative Strategies. While we expect that improved anterior segment biometry measurement with OCT will improve cataract surgery outcomes in those with prior LASIK, additional parameters could potentially further reduce the IOL prediction error. For instance, as described earlier, modern

[figure not shown]

FIGURE 8. Overview of primary clinical outcome to determine if more accurate anterior segment biometry measurement from OCT improves post-LASIK cataract surgery refractive outcomes. Before cataract surgery (left column), we will calculate the needed intraocular lens (IOL) power via (1) standard of care (SoC: 21.0 D in this example) and via (2) our OCT based corneal power and anterior segment biometry measurement (20.5 D). The surgeon will perform cataract surgery and implant an IOL (21.0 D IOL). Based on the post-operative refraction, the power actually needed for a plano result will be calculated (20.25 D). The difference between this calculated reference and the predicted power is the prediction error. We will compare the proportion of SoC and OCT results with prediction errors ≤ 0.50 D.

IOL power formulas estimate the final position of the IOL by using the corneal curvature. Interestingly, in recently presented preliminary data [50], a formula which did not utilize corneal curvature for estimating the lens position [51] appeared to do better than those that did use corneal curvature in post LASIK patients undergoing cataract surgery. In our study, we will be obtaining additional biometric measurements pre and post-op – both standard of care and OCT based – to be able to analyze other contributions to the IOL error if there is a systemic bias even after corneal power correction. Regression to these collected data and measurements could be utilized as an alternative approach [45].

Alternatively, other commercially available spectral domain OCT could be used for this aim. However, they currently lack the imaging range necessary to perform the anterior segment biometry required for this aim, and they generally cannot provide a reference axis to the fovea for their corneal measurements. Conversely, the corneal power specific portions of our algorithms could be applied to existing OCT to improve their corneal power measurements and benefit the clinical OCT community in general.

Specific Aim 3: Develop and validate algorithms to produce accurate three-dimensional posterior eye OCT reconstructions to supplant MRI for measuring posterior eye shape in myopia applications.

SA3. Introduction. Current clinical OCT images of the posterior eye are spatially inaccurate. This can be observed simply by noting that almost all clinical OCT images of the retina appear artificially flattened when the expectation is that the eye globe should be curved (Fig. 9). Because of this spatial inaccuracy, OCT cannot in its current form replace MRI for the quantitative study of ocular shape deviations in diseases such as myopia, even though OCT is more clinically accessible and has higher spatial resolution than MRI. Further, the spatial inaccuracy with OCT is compounded by variable optical artifacts from the system and eye, meaning that image differences between patients or time points may not be solely due to pathology as is usually assumed.

The spatial inaccuracy of current posterior eye OCT images results from the current standard practice of simply displaying A-scans next to each other in a parallel fashion. This fails to account for the actual, non-parallel transit of OCT light through the eye. The objective of this aim is two-fold. The *first objective* is to develop and validate algorithms for accurately portraying the posterior eye in OCT images by ray tracing the OCT imaging paths through the imaged anterior eye. The *second objective* is to then test the hypothesis that corrected posterior eye OCT images will be comparable to MRI of the same eyes.

The *rationale* for this aim is that successful completion of this aim will produce posterior eye OCT images faithful enough to replace MRI imaging for studying posterior eye shape biomarkers. Our expectation is that this development will remove cost and logistical barriers limiting more widespread study of posterior eye shape as a diagnostic biomarker for myopia progression, particularly in children and young adults.

SA3. Justification & Feasibility. In an initial study by the P.I. [4], we enrolled subjects in an IRB approved study who had recently obtained head MRIs for their medical care but did not have ocular disease. We performed ocular biometry and retinal

[figure not shown]

FIGURE 9. Representative original and spatially (numerically) corrected retinal OCT B scans (top R) and comparison to MRI (bottom L and R) [4]. The posterior eye appears flat in the original image (top L) and has a more plausible physiologic curvature after spatial correction (top R). Reported values in the literature for posterior eye curvature (R_c) range from 10.8-14.1 mm [34]. Spatial correction in the 10 eyes in this study significantly reduced the difference between OCT and MRI posterior eye shape (bottom L). In this small preliminary study, there remains a bias and a possible trend between the OCT measures and MRI (bottom R).

SDOCT on these subjects. Using commercial ray tracing software, we modeled the commercial SDOCT system and the subjects' eyes using their measured biometric data. The spatial orientation of the OCT scan paths was then used to reorient each OCT A-scan to its modeled location in MATLAB. Using this correction, there was a significant reduction in differences and variability between posterior eye shape measured by OCT and MRI (Fig. 9).

Despite the overall improvement in posterior eye OCT shape in this pilot study, there remained a bias between the OCT measures and MRI. The possible sources of error in this preliminary work (other than small

sample size) include the lower resolution of these non-orbital MRI scans, the use of schematic model anterior eyes, motion errors, and the unknown system-to-cornea distance to control for scan magnification.

In this proposal, we will perform a prospective study with dedicated orbital MRIs, with measured and model-free determination of all ocular surfaces, with decreased patient motion from the faster SSOCT system, and with direct measurement of the system-to-cornea distance (see SA1.Research Design.System Calibration). With these improvements, we anticipate that we will decrease the curvature difference between MRI and OCT to less than a millimeter (resolution of our MRI). Further, we will compare surface topographies of myopic patients with known morphometric changes (e.g. staphylomas) imaged with MRI and OCT.

SA3. Research Design. Algorithm development and validation. We will extend our previously developed three-dimensional refraction correction algorithms [20] to perform ray tracing of the OCT scan paths through the ocular surfaces contained within the whole eye OCT images. The anterior eye image content will be segmented and corrected of optical distortions as in Aim 2 (refraction, non-telecentricity, motion). Group refractive indices for our light source ($\lambda_0 = 1060$ nm) will be used for refraction correction as described in detail in SA2.Research Design.Algorithm Development. For the lens, we will measure the group index for IOLs, and use a polynomial model for natural lenses [52] as was used in our pilot work [4]. The retinal layers of the posterior eye will also be segmented in preparation for post-processing [53]. With a known system topology, measured and hence known system-to-cornea distance per patient, and an accurate representation of the anterior eye components, we will determine the spatial orientation of the OCT scan paths to the posterior eye. With these OCT scan paths, the posterior eye A-scans will be properly repositioned spatially to restore anatomic accuracy.

We will validate the algorithms by imaging a constructed model eye. The model consists of a custom-made +30 D rigid gas permeable contact lens (Essilor, center thickness 490 μm), a +20 D intraocular lens (SA60AT, Alcon), and a glass hemisphere with a 12.5 mm radius of curvature (64-496, Edmund Optics). These will be mounted into a lens tube at physiological distances and then immersed into balanced salt solution, leaving only the anterior surface of the contact lens ("cornea") exposed. The model eye will be imaged with the whole eye OCT and the surfaces recovered. After correction with the above algorithms, the curvature of the hemisphere will be compared to that of the manufacturer reference.

Clinical study. For the clinical studies, we will enroll two groups of subjects: 1. pseudophakic subjects with no known history of ocular pathology other than refractive error (no more than -6 D) and 2. pseudophakic and phakic subjects with high progressive myopia including those with staphylomas.

Group 1. The goal for the first group is to demonstrate in a normal eye the ability to accurately recreate the posterior eye with OCT spatially comparable to MRI (Fig. 10). We will only include monofocal pseudophakic individuals in this group. This reduces uncertainties by using a known manufactured lens. At the Duke Eye Center, the monofocal lens of choice is manufactured by Alcon, and the company has provided us with the optical prescriptions of their IOLs for research use under a non-disclosure agreement. With the optical properties of the IOL known, we anticipate being able to fully characterize these normal, pseudophakic eyes optically. This also provides a baseline from which phakic eyes can be studied.

Each enrolled subject will undergo the following imaging: optical biometry (LenStar, Haag-Streit), whole eye OCT, and MRI imaging. MRI will be performed on the clinical research scanners at the Duke Brain Imaging and Analysis Center (see support letter from director [name]). Annually, with the assistance of dedicated research coordinators, they image over 2000 subjects with MRI for over 70 research projects. Their scanner (GE) has a magnetic field strength of 3.0 Tesla. A high resolution T1 FSPGR sequence will be used to acquire images of the subject's eyes. Images will be acquired in the axial plane, with FOV=25.6cm, TR=8ms, TE=3ms, flip angle=12, 512x512x50 imaging matrix, completely covering the eyes. A second T2 weighted sequence will be acquired at the same slice prescription with TR=3s and TE=25ms. With these scan parameters, each voxel will be 0.5 mm^3 . During scanning, a fixation target will be provided to minimize eye motion during acquisition.

[figure not shown]

FIGURE 10. General overview of clinical study design to determine the difference between OCT and MRI posterior eye images. Using radius of curvature as a general measure of shape, we will compare the paired differences between the two modalities. In a second study in subjects with staphylomas, we will use root mean square difference to describe the topographic differences between the two registered modalities.

The radius of curvature of the posterior eye will be measured via surface fitting of the posterior eye data from OCT and MRI. To have 80% power to detect a 0.5 mm difference in radius of curvature between OCT and MRI using a paired one-sample t-test, we will need to enroll a minimum of 48 normal pseudophakic subjects (PROC POWER, SAS v9.3). This power calculation assumes that with our whole eye OCT and improved algorithms, we will halve the standard deviation of the difference between MRI and OCT found in our initial study (2.3 mm), resulting in an estimated standard deviation of 1.2 mm. At a 0.5 mm difference, we will be at the effective voxel resolution of the MRI scans and should also have more than enough resolution to identify the large-scale topographic abnormalities noted in previous MRI studies of myopia [25,26].

Group 2. After enrollment and data analysis of the first group, we will then examine the ability of OCT to provide spatially comparable images to MRI in eyes that are structurally abnormal. We will enroll 20 adult patients with progressive high myopia (more than -6 D) especially targeting those with posterior staphylomas – outpouchings of the posterior eye. These subjects can be pseudophakic or phakic. Phakic subjects will be required to be cyclopleged to ensure no dynamic lens changes during imaging. For phakic reconstructions, we will use age appropriate models of the natural lens indices as we have used in our previous study [52]. After recovery of the OCT and MRI surfaces, the OCT surface will be registered to the MRI surface at a common feature (e.g. optic nerve) and via cross-correlation. A root mean square deviation across the registered surfaces will then be calculated to quantify the topographic difference between the OCT and MRI surfaces.

SA3. Expected Outcomes. At the conclusion of this aim, we will have developed algorithms to spatially correct full eye OCT images and validated them with reference phantoms. We will also have tested the idea that spatially corrected OCT images will be comparable to MRI representations of the posterior eye first in pseudophakic normal eyes and then in pseudophakic and phakic myopic eyes. This will provide the basis for OCT to replace MRI for ophthalmic studies of ocular morphometry, lowering cost and logistical barriers to these types of studies while also providing higher resolution images over MRI. This has clinical utility for study of myopia progression and risk stratification based on prior studies associating deviations in ocular shape with pathologic myopia.

SA3. Potential Problems & Alternative Strategies. The FOV of our proposed posterior eye OCT channel will be 85° (or ~120° relative to center of the eye) – at least double that of standard retinal photography. This should be sufficient for measuring posterior eye shape as it encompasses the entire macula and reaches nearly to the equator of the eye. Should larger FOV be desired, though, we can use montaging as others have shown with OCT [54] to further increase our FOV. Because our whole eye OCT also concurrently images the anterior eye, our reconstructions can account for the relative change in position between the system and the eye to increase the accuracy of montaging and provide additional references for montage reassembly.

While the natural lens does present an ambiguity, by first imaging pseudophakic subjects in group 1 and part of group 2, we will first refine and validate our algorithms independent of the natural lens. This lays the foundation for subsequently investigating and isolating any differences between MRI and OCT resulting from imaging phakic subjects in group 2. Our preliminary algorithm using a polynomial gradient index lens model [52] demonstrated reduced differences between OCT and MRI [4]. Alternate OCT based natural lens models [55] can be incorporated into our reconstructions for reanalysis of captured and stored image data if necessary. Our use of these gradient indices is far more sophisticated than the average refractive indices successfully used for ocular axial biometry both in research and clinically [56,57 and commercially available partial coherence interferometers]. If necessary, we can similarly use average indices. Importantly, with the validated pseudophakic group, we will be able to compare and contrast quantitative performance of OCT in phakic subjects. This data has important implications for both the OCT and myopia communities.

Timetable. We anticipate this ambitious project will require the full requested five year project period to complete. We anticipate the whole eye SSOCT system design and assembly will take approximately one year. Algorithm development will begin with initial images of phantoms and normals and can occur concurrently with clinical imaging because all acquired images can be post-processed at a later date if necessary. Data collection, data analysis, and publication will occur on a rolling basis throughout the project.

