Time-domain OCT (Zeiss Visante) was one of the first OCT devices used for the purpose of anterior segment biometry [36]. However, motion artifacts due to its slow acquisition rate reduced the reliability of its measurements [7]. With the substantial speed and resolution increase from spectral-domain OCT, accurate spherical corneal power measurements have been shown [34,36]. Compared to clinical standards, though, the P.I. has shown that the standard deviation of SDOCT measures was higher than clinical resolution [37]. With dedicated motion correction techniques, this variability decreased to clinical resolution [32], suggesting the speed of conventional SDOCT alone was not sufficient to mitigate motion artifacts. With motion correction, we were also able to measure true OCT based corneal topography [38]. This global corneal surface measurement has not been available with clinically available OCT systems likely due in part to motion artifacts. Also, in contrast to the slower Visante, the limited depth range of SDOCT does not allow the measurement of anterior segment biometry as used in OCT based intraocular lens selection [36].

The objective of this aim is two-fold. The *first objective* is to develop and validate algorithms for the accurate measurement of anterior segment biometry from OCT images including clinical corneal spherical and astigmatic powers and anterior segment dimensions (such as anterior chamber depth and width). The *second objective* is to test the hypothesis that improved anterior segment biometry measurement with OCT will improve cataract surgery outcomes in patients with prior LASIK.

The *rationale* for this aim is that successful completion of this aim will produce OCT images of the anterior eye faithful enough for accurate anterior segment biometry. In addition to the clinical rationale, this aim also serves to validate anterior segment measures for the posterior segment aim. Our *expectation* is that the more accurate measurement of anterior segment biometry will remove uncertainty in optical characterization of the post-LASIK eye and improve cataract surgery outcomes in this population.

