SA2. Research Design. *Algorithm development and validation.* In contrast to the SDOCT system that we used for our preliminary data above, the proposed whole eye SSOCT system will provide deeper and wider anterior eye views, while simultaneously imaging the posterior eye. There are multiple benefits to this. First, imaging more of the anterior eye will allow for complete anterior segment biometry measurements which can be used to improve intraocular lens selection [41-45]; the cornea alone is not the only determinant of intraocular lens power. Secondly, the co-registered posterior eye image from whole eye OCT will also allow for definition of the visual axis to provide a functional reference axis for the corneal power measurement.

With the raw anterior eye OCT images, the following post-processing algorithms will be applied: segmentation of ocular surfaces, removal of optical and motion artifacts, and finally recovery of the desired clinical parameters. For segmentation, we will use our prior dynamic programming based algorithms [39] and modify them to account for the wider FOV in the whole eye OCT system. In addition, these intensity and graph based algorithms will be extended to segment the iris surface to identify the pupil location.

For removal of optical artifacts, we will directly apply our prior, validated three-dimensional refraction correction algorithms [20]. Successful 3D refraction correction requires accurate characterization of sample arm scanning geometry, sample space, and refractive indices. The scanning geometry is known from our Zemax design, and sample space will be calibrated as described in Aim 1 and [20]. Refractive indices for OCT based refraction correction requires knowledge of the group (not phase) refractive index at the wavelength of interest. Co-Investigator [name], in collaboration with OCT inventor [name], first described physical measurement of the group refractive index of samples (such as the cornea) using OCT in 2004 [46]. Briefly, a cuvette of known, calibrated internal chamber thickness is imaged and measured first. Then a representative sample (for example, calibration phantom or fresh *ex vivo* cornea) is placed in the chamber and the thickness is re-measured. The image provides the resultant optical pathlength change of the chamber as a result of the

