Clinical study. We will enroll subjects who have had previous laser refractive surgery (LASIK, PRK) and who will be undergoing cataract surgery to test the hypothesis that improved corneal power measurement using OCT will improve the refractive outcomes compared to standard of care (Fig. 8). Each enrolled subject must be able to have optical biometry measurements (IOLMaster, Carl Zeiss Meditec) needed for standard of care IOL selection. The optical biometric measurements include corneal power (K), anterior chamber depth (ACD), and axial length (AL) among others. These subjects will also be imaged with the whole eye OCT system. We will then choose two intraocular lens powers predicted to achieve a near emmetropic (plano) outcome:

1. Standard of care (SoC) based on the Haigis-L output recommendation at <http://iol.ascrs.org>. This IOL calculator website for post refractive surgery eyes is maintained by the American Society of Cataract and Refractive Surgeons (ASCRS) and is readily available to the clinical community. The website has multiple formulas but only two – the Haigis-L and the Shammas-PL – do not require prior records. This is most comparable to an OCT based method which also would not require prior records. We are choosing the Haigis-L because there are prior results in the literature from a small pilot study directly comparing the Haigis-L to a different corneal SDOCT based method [45] which can be used to power our study.

2. Whole eye OCT based. We will use the OCT based vergence tracing formula described in [36]. Current clinical IOL formulas have many assumptions inherent in them such as a non-surgically altered cornea and that estimated lens position is a function of the non-surgically altered cornea [47]. To remove these assumptions which are violated in post LASIK patients, we will recover the pertinent biometry measures directly from whole eye OCT and use the described vergence tracing formula to determine the whole eye OCT recommended IOL. This formula was developed specifically for OCT, but available time domain OCT at that

[figure not shown]

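### Aim 2 words its hypothesis and expected conclusion as an effect of better OCT measurement, but its comparison changes measurement source and IOL formula together and supports only a claim about the complete methods

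*Combined protocol and SAP*

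**What the plan says.** Four places in the Aim 2 text give measurement as the thing being tested or shown:

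- SA2. Introduction, second objective: "to test the hypothesis that improved anterior segment biometry measurement with OCT will improve cataract surgery outcomes in patients with prior LASIK".
- SA2. Research Design, Clinical study: "to test the hypothesis that improved corneal power measurement using OCT will improve the refractive outcomes compared to standard of care".
- Figure 8 caption, on the purpose of the primary clinical outcome: "to determine if more accurate anterior segment biometry measurement from OCT improves post-LASIK cataract surgery refractive outcomes".
- SA2. Expected Outcomes, on what the study will deliver: "clinical data to support the idea that accurate measurement of anterior segment biometry will improve cataract surgery refractive outcomes".

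The Clinical study section then defines two predictions per eye. Standard of care is the Haigis-L recommendation, with IOLMaster optical biometry as its measurement source. The OCT prediction takes biometry from whole eye OCT and puts it through a published vergence tracing formula developed for OCT. The section explains the change of formula: "Current clinical IOL formulas have many assumptions inherent in them such as a non-surgically altered cornea". It presents direct OCT measurement and the vergence formula jointly as the way to remove those assumptions.

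The primary analysis compares, within eyes, the proportions of predictions within ±0.50 D of a reference power calculated back from the month 1 manifest refraction. The null hypothesis is equal proportions for the two methods, and the test is a conditional McNemar test.

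**The concern.** A hypothesis about measurement calls for a contrast in which measurement changes and the rest of the calculation does not. Here the formula changes as well, and the plan expects the formula to matter. SA2. Potential Problems & Alternative Strategies cites preliminary data in post-LASIK eyes where a formula that did not use corneal curvature to estimate lens position appeared to do better than formulas that did.

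If the OCT method wins, the wording invites the conclusion that more accurate biometry improved the result, although some or all of the gain might come from the formula. If there is no difference, better biometry might have been offset by the formula; this is only a possibility, and the documents give no figure for it. The distinction has practical weight. The same section suggests applying the corneal power algorithms to existing OCT devices, and any gain in IOL prediction from that step would depend on what measurement contributes by itself.

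**Working it through.** **1. The plan's own figure.** Inputs, all from the sample size paragraph of the Clinical study section: p1 = 0.4198 (SoC), p2 = 0.6875 (OCT), n = 60, α = 0.05 two-sided, pair correlation r = 0, 0.2 or 0.4.

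The probability that both predictions fall within ±0.50 D is p11 = p1·p2 + r·√(p1(1−p1)p2(1−p2)). Here p1·p2 = 0.2886, and the root is √(0.2436 × 0.2148) = 0.2288. The OCT-only probability is p2 − p11 and the SoC-only probability is p1 − p11. Exact conditional McNemar power is averaged over the binomial number of discordant pairs.

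| r | OCT only | SoC only | Exact power | Plan |
|---|---|---|---|---|
| 0 | 0.399 | 0.131 | 78.7% | 80% |
| 0.2 | 0.353 | 0.085 | 87.4% | 88% |
| 0.4 | 0.307 | 0.040 | 96.1% | 96% |

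The stated power reproduces to within 2 points. Nothing in this point changes it.

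**2. What differs between the methods.**

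| | SoC | OCT |
|---|---|---|
| Measurement source | IOLMaster | whole eye OCT |
| Formula | Haigis-L | vergence tracing |

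Let H be the Haigis-L formula, V the vergence formula, a the IOLMaster inputs and b the OCT inputs. The compared predictions are H(a) and V(b). Formally,

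V(b) − H(a) = [V(b) − V(a)] + [V(a) − H(a)].

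The first bracket is a measurement effect and the second a formula effect. The plan calculates neither V(a) nor H(b), so only the sum is observed. Whether V(a) can be calculated at all depends on the inputs of a formula that the documents cite but do not set out.

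**3. The Figure 8 example.** SoC is 21.0 D, OCT 20.5 D and the reference 20.25 D. The SoC error is 21.0 − 20.25 = 0.75 D, outside the limit. The OCT error is 20.5 − 20.25 = 0.25 D, inside it. This eye counts for OCT because the predictions differ by 21.0 − 20.5 = 0.50 D, and the example does not show which component produced that difference. It illustrates the point and does not measure it.

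**4. The planning effect.** The difference is 68.75 − 41.98 = 26.77 percentage points. The OCT proportion comes from a pilot of a different OCT-based method. The assumed effect is therefore itself between complete methods and says nothing about a measurement-only effect.

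**5. Whether other planned work fills the gap.** The phantoms and the 20 normal subjects check accuracy of the anterior eye algorithms, not IOL prediction error in post-LASIK eyes. The repeat post-operative biometry and OCT address final lens position and the relation between devices. The analysis of other contributions to IOL error is conditional on bias remaining after corneal power correction, and it does not separate measurement from formula.

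**The case against.** The best defence is that the plan already tests methods. The Clinical study section names both formulas openly, the null hypothesis concerns the two methods' proportions, and even the stated hypothesis is relative to standard of care, which is then defined as the Haigis-L output. The pairing is also deliberate: the formula was developed for OCT, and the plan treats direct measurement and vergence tracing as one mechanism. The Figure 8 caption is a summary that names neither formula, and Expected Outcomes speaks only of supporting an idea.

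Most of this stands. It shows that the design and test are coherent, and it makes the point minor. It does not justify naming measurement as the cause: if the two components work as one mechanism, the conclusion should be about that mechanism.

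A reader might infer more than the documents support:

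- *That the primary test is invalid or underpowered.* It is valid at method level, and the power reproduces.
- *That corneal power in one place and anterior segment biometry in another are conflicting hypotheses.* SA2. Introduction defines the biometry to include corneal powers and calls corneal power the factor thought to predominate. The Research Design remark that "the cornea alone is not the only determinant of intraocular lens power" is consistent with that.
- *That the number of discordant eyes sizes the problem.* Those counts restate the power inputs and would be the same if measurement alone changed.
- *That a same-formula analysis must be added.* Its feasibility depends on inputs the documents do not give, and substituting keratometric values would not cleanly isolate measurement.
- *That the formula, not the measurement, would explain a win.* The documents do not establish this either.

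**Conclusion.** The point holds as a minor correction to the wording of the hypothesis and conclusion. The comparison can show whether one complete prediction method places more eyes within ±0.50 D than the other. It cannot show that better measurement is the reason, and a null result would not show that better measurement is without value. No numerical size can be given to the over-attribution, because nothing in the documents apportions the 26.77 points. The conclusion rests on the two methods being applied as the Clinical study section describes, and on there being no planned analysis that fixes one component, which is so in the text provided.

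**What to change.** In the second objective (SA2. Introduction), the Clinical study hypothesis, the Figure 8 caption and SA2. Expected Outcomes, restate the question and the expected conclusion as whole eye OCT biometry with vergence tracing versus IOLMaster biometry with Haigis-L, judged by the proportion of eyes with IOL power prediction error within ±0.50 D. Say once, in the Clinical study section, that measurement source and formula change together by design and that no measurement-specific effect will be claimed from this comparison.

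The endpoint, test, sample size, visits and power stay as they are. The cost is an edit in four places and a narrower headline claim.
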